4.2 Exclusion Criteria

1. Subject enrolled in a study to investigate a treatment for COVID-19
2. Requires mechanical ventilation
3. Subject taking an anti-androgen of any type including: androgen deprivation therapy, 5-alpha reductase inhibitors, etc...
4. Patients who are allergic to the investigational product or similar drugs (or any excipients);
5. Subjects who have malignant tumors in the past 5 years, with the exception of completed resected basal cell and squamous cell skin cancer and completely resected carcinoma in situ of any type
6. Subjects with known serious cardiovascular diseases, congenital long QT syndrome, torsade de pointes, myocardial infarction in the past 6 months, or arterial thrombosis, or unstable angina pectoris, or congestive heart failure which is classified as New York Heart Association (NYHA) class 3 or higher, or left ventricular ejection fraction (LVEF) $< 50\%$, QTcF > 450 ms
7. Subjects with uncontrolled medical conditions that could compromise participation in the study (e.g. uncontrolled hypertension, hypothyroidism, diabetes mellitus)
8. Known diagnosis of human immunodeficiency virus (HIV), hepatitis C, active hepatitis B, treponema pallidum (testing is not mandatory)
9. Alanine Transaminase (ALT) or Aspartate Transaminase (AST) > 5 times the upper limit of normal.
10. Estimated glomerular filtration rate (eGFR) < 30 ml/min
11. Severe kidney disease requiring dialysis
12. Women of child-bearing potential, defined as all women physiologically capable of becoming pregnant, unless they are using highly effective contraception, as shown below, throughout the study and for 3 months after stopping GT0918 treatment. Highly effective contraception methods include:
 - Total Abstinence (when this is in line with the preferred and usual lifestyle of the patient. Periodic abstinence (e.g. calendar, ovulation, symptothermal, post-ovulation methods) and withdrawal are not acceptable methods of contraception, or

- Use of one of the following combinations (a+b or a+c or b+c):
 - a: Use of oral, injected or implanted hormonal methods of contraception or other forms of hormonal contraception that have comparable efficacy (failure rate < 1%), for example hormone vaginal ring or transdermal hormone contraception.
 - b: Placement of an intrauterine device (IUD) or intrauterine system (IUS) ;
 - c: Barrier methods of contraception: Condom or Occlusive cap (diaphragm or cervical/vault caps) with spermicidal foam/gel/film/cream/vaginal suppository ;
 - Female sterilization (have had prior surgical bilateral oophorectomy with or without hysterectomy) or tubal ligation at least six weeks before taking study treatment. In case of oophorectomy alone, only when the reproductive status of the woman has been confirmed by follow-up hormone level assessment ;
 - Male sterilization (at least 6 months prior to screening). For female patients on the study, the vasectomized male partner should be the sole partner for that patient;
 - In case of use of oral contraception women should have been stable for a minimum of 3 months before taking study treatment. Women are considered post-menopausal and not of child bearing potential if they have had 12 months of natural (spontaneous) amenorrhea with an appropriate clinical profile (e.g. age appropriate, history of vasomotor symptoms) or have had surgical bilateral oophorectomy (with or without hysterectomy) or tubal ligation at least six weeks ago. In the case of oophorectomy alone, only when the reproductive status of the woman has been confirmed by follow up hormone level assessment, is she considered not of child bearing potential;
13. Sexually active males must use a condom during intercourse while taking the drug and for 3 months after stopping GT0918 treatment and should not father a child in this period. A condom is required to be used also by vasectomized men in order to prevent delivery of the drug via seminal fluid
14. Subject likely to transfer to another hospital within the next 28 days
15. Subject (or legally authorized representative) not willing or unable to provide informed consent

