***No interaction has been reported between Proxalutamide, nitazoxanide, and azithromycin.**

Table 1.2.3: Inhibitory Effect of Proxalutamide on CYP450 Enzymes

CYP450s	Probe substrate	Characterized Metabolic Pathway	Characterized Metabolite	IC ₅₀ (μM)
CYP1A2	Phenacetin	Deethylation	Acetaminophen	>200
CYP2C9	Tolbutamide	Hydroxylation	4-Hydroxy-Tolbutamide	8
CYP2C19	Omeprazole	Hydroxylation	5-Hydroxy- Omeprazole	8
CYP2D6	Dextromethorphan	Demethylation	Dextrorphan	5
CYP3A4	Midazolam	Hydroxylation	1-Hydroxy-Midazolam	56
CYP3A4	Testosterone	Hydroxylation	6β-Testosterone	1
CYP2E1	Chlorzoxazone	Hydroxylation	6-Hydroxy-Chlorzoxazone	>200

Evaluation of Cytochrome P450 Induction Potential of Proxalutamide in Human Hepatocytes

Proxalutamide was evaluated for induction of drug metabolizing enzymes in primary human hepatocytes. No inductive effects on CYP1A2 and CYP3A4 were observed in the level of enzymatic activity.

Table 10: Effect of Proxalutamide on the Enzyme Activity of CYP1A2

	Activity of CYP1A2 (%)			Mean	SD	Activity compared to positive control (%)
Negative control	109	82.4	108	100	15.2	NA
Positive control	1174	1246	1207	1209	36.3	100
Proxalutamide 1 μM	98.9	98.2	95.6	97.6	1.74	<40
Proxalutamide 10 μM	92.3	98.9	99.6	96.9	4.01	<40

Table 11: Effect of PROXALUTAMIDE on the Enzyme Activity of CYP3A4

Control	Activity of CYP3A4(%)			Mean	SD	Activity compared to positive control(%)
Negative control	97.3	103	99.6	100	2.97	NA
Positive control	805	976	825	869	93.4	100
Proxalutamide 1 μM	24.2	26.0	27.7	26.0	1.73	<40
Proxalutamide 10μM	19.7	21.3	19.4	20.2	1.05	<40

Specific Populations

Pediatric

Proxalutamide pharmacokinetics have not been investigated in subjects younger than 18 years.

Geriatric

No dose adjustment is necessary in the elderly. The pharmacokinetics and pharmacodynamics of Proxalutamide were evaluated in 40 patients with an average age of 70.1 (Study 2, Section 1.1.2.4.).

Gender

Proxalutamide is not indicated for use in women. The planned interventional study will be conducted in men only.

Race

The effect of race on Proxalutamide pharmacokinetics has not been studied.

Renal Impairment

The effect of renal impairment on Proxalutamide pharmacokinetics has not been studied.

Hepatic Impairment

The effect of hepatic impairment on Proxalutamide pharmacokinetics has not been studied.

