4.1 Inclusion Criteria

1. Admitted to the hospital with symptoms of COVID-19
2. Male and females age ≥ 18 years old
3. Laboratory confirmed positive SARS-CoV-2 rtPCR test within 7 days prior to randomization or confirmed lung involvement by CT scan
4. Clinical status on the COVID-19 Ordinal Scale (defined in Section 5.1) of 3 to 6
5. Coagulation: INR $\leq 1.5 \times \text{ULN}$, and APTT $\leq 1.5 \times \text{ULN}$
6. Subject (or legally authorized representative) gives written informed consent prior to performing any study procedures
7. Subject (or legally authorized representative) agree that subject will not participate in another COVID-19 trial while participating in this study

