6.1 Safety Parameters

Safety parameters will be assessed as follows:

I. Physical Examination:

The PI will conduct a thorough physical examination during screening. The assessment will be recorded in the appropriate CRF.

II. Clinical Laboratory Evaluations:

The following tests will be conducted: WBC, differential, Hgb, PLT, creatinine, glucose, total bilirubin, AST, ALT and coagulation PT.

III. Adverse Events:

Safety will be assessed by summarizing the incidence and type of Adverse Events in a CRF form.

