6.3.11 Reporting of Pregnancy

Pregnancy is not defined as an AE. However, any pregnancy that occurs during study participation should be reported to the sponsor on the appropriate CRF. Pregnancy should be followed to outcome.

6.4 *Unanticipated Problems*

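### The amended protocol enrols women but does not explicitly exclude pregnancy or breastfeeding at entry, schedules no pregnancy test, and in one paragraph still limits the study to men

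*Combined protocol and SAP*

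**What the plan says.** All references are to the amended protocol, the version with the female cohort, unless stated otherwise.

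Inclusion 2 in Section 4.1 admits "Male and females age ≥ 18 years old", and Section 1.4 plans 300 men and 300 women. Exclusion 12 in Section 4.2 removes "Women of child-bearing potential, defined as all women physiologically capable of becoming pregnant, unless they are using highly effective contraception", with contraception to continue through the study and for 3 months after treatment. One route that satisfies it alone is "Total Abstinence (when this is in line with the preferred and usual lifestyle of the patient". The others are pairs drawn from hormonal, intrauterine and barrier methods, and female or male sterilization. Oral contraception carries a look-back: "In case of use of oral contraception women should have been stable for a minimum of 3 months before taking study treatment".

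Section 6.1 gives the laboratory list: "The following tests will be conducted: WBC, differential, Hgb, PLT, creatinine, glucose, total bilirubin, AST, ALT and coagulation PT". Section 6.2 places these tests at admission and at day 14, and leaves any others to the investigator. Section 6.3.11 says "any pregnancy that occurs during study participation should be reported to the sponsor on the appropriate CRF", and asks that the pregnancy be followed to its outcome.

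Under Specific Populations, the Gender paragraph says: "Proxalutamide is not indicated for use in women. The planned interventional study will be conducted in men only".

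**The concern.** Exclusion 12 looks forward. It asks how a woman will avoid becoming pregnant, not whether she is pregnant on the day she is randomized. With no scheduled test, an early pregnancy that neither she nor the investigator knows about would not be found before the first dose.

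The protocol itself treats fetal exposure as something to prevent. It extends contraception for 3 months beyond treatment, requires condoms even of vasectomized men so that drug is not passed on in semen, and counts congenital anomaly among serious outcomes in Section 6.3.2. An entry rule that leaves direct dosing of a pregnant woman unchecked does not serve that aim, and the harm could not be repaired at analysis.

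The Gender paragraph is a separate and smaller defect. Sites and ethics committees are given two incompatible descriptions of who may be enrolled.

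**Working it through.** No formula in the plan is involved, so the check is a reading of the criteria and the schedule.

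1. **Criteria.** In Sections 4.1 and 4.2, exclusion 12 is the only item bearing on pregnancy. It covers contraceptive methods, sterilization and menopausal status. Current pregnancy and breastfeeding are named nowhere in either list.

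2. **Applying exclusion 12 as written** to women who meet all other criteria:
   - *Unrecognised early pregnancy, using a listed method.* She is eligible. Abstinence has no stated look-back period, and neither does a pair such as an intrauterine device with a condom. Look-backs are given for oral contraception (3 months), female sterilization (six weeks) and male sterilization (6 months before screening).
   - *Pregnant, and qualifying through abstinence or another listed method.* She meets the letter of the criterion.
   - *Known to be pregnant, using no listed method.* Section 4.2 treats a woman as not of child-bearing potential after 12 months of natural amenorrhea with a fitting clinical profile, or after oophorectomy or tubal ligation. A pregnant woman would ordinarily meet none of these, so she is probably still of child-bearing potential and excluded. The definition by capability of becoming pregnant leaves this unsettled.
   - *Breastfeeding, using accepted contraception.* No text excludes her.

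3. **Tests.** The Phase I steps in Section 3.2 are eligibility review, physical examination, consent, numbering, randomization, treatment and recording. The Section 6.1 list has no pregnancy test, and Section 6.2 adds none.

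4. **Timing.** Laboratory tests are done at admission (Section 6.2). Enrolment may come up to 5 days after admission (Section 3.2).

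5. **Statements of sex.** The Gender paragraph says men only. Section 1.4 (300 women), Section 2 (male and female patients), Section 3.2 (cohorts of men and women) and inclusion 2 in Section 4.1 say otherwise. The same Gender sentence stands in the male-only version, where it was consistent. The revision history dates the female cohort to January 10, 2021 and the sexual-activity exclusions to January 11, 2021.

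6. **Size.** The documents do not give the share of women of child-bearing potential. Taking 20-40% as an assumption:
   - 300 × 0.20 = 60 and 300 × 0.40 = 120 women entering with no scheduled check
   - at 1:1 allocation, 60 / 2 = 30 to 120 / 2 = 60 of them on active drug

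   These are untested women, not pregnancies. The documents give no pregnancy prevalence, so the number of pregnancies at first dose cannot be derived.

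**The case against.** The defence has five arguments.

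- **Known pregnancy.** A reader might infer that a woman known to be pregnant falls outside exclusion 12 because she cannot become pregnant. The documents do not support this: Section 4.2's own account of who is not of child-bearing potential does not include her. Without abstinence or sterilization she would need two concurrent methods, so many known pregnancies would be caught. This stands, and it narrows the gap to unrecognised pregnancy, pregnancy in a woman who qualifies by a listed method, and breastfeeding.

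- **The laboratory list.** Section 6.1 is a safety list, not a full screening list. Eligibility also uses APTT, rtPCR or CT, QTcF and LVEF, none of which appears there. Medical history, physical examination and the investigator's freedom to order tests give partial cover. This also stands, so absence from Section 6.1 alone would prove little. But those other measurements are each required by a criterion in Section 4.1 or 4.2, and no criterion calls for a pregnancy test. Discretionary testing is not an eligibility rule.

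- **Pregnancy on study.** A reader might infer that a pregnancy present at entry could not be told apart from one that began later. That goes too far. Section 6.3.11 requires follow-up to outcome, and dating could often separate the two. It does not prevent the first dose from being given.

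- **Breastfeeding.** The documents contain no lactation data, so they support asking for a stated position but not a conclusion about what it should be.

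- **The Gender paragraph.** It is leftover text, and inclusion 2 is the operative rule. That is fair: it needs editorial reconciliation and does not carry the main point.

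The consent form was not available and may mention pregnancy. It would not replace a criterion in Section 4.2.

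**Conclusion.** The concern holds within these limits. As written, the amended protocol can admit a woman with an unrecognised pregnancy, or a pregnant woman who qualifies through abstinence or another listed method, without breaching any criterion. Breastfeeding is not addressed at all. Confidence is high for the textual absences and for the men-only contradiction. It is lower for how sites would treat a known pregnancy in a woman using no listed method.

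The 60-120 figure might be read as the number of exposed pregnancies. It is not. It rests on the assumed 20-40% share, and the number of pregnancies could be very small, since these women must already meet the contraception conditions. The case for correction rests on the mismatch with the protocol's own aim and on the low cost of the remedy, not on a count. The point should be fixed before women are enrolled.

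**What to change.** - **Section 4.2.** State explicitly that women pregnant at entry are not eligible, in line with the protocol's own aim of preventing fetal exposure, and state the position on breastfeeding.
- **Section 3.2 Phase I and Sections 6.1/6.2.** Add a pregnancy test before randomization for women of child-bearing potential, with the sponsor setting the window. A reader might assume the admission sample will always serve. With enrolment possible up to 5 days later it may not, and a separate urine test may be needed.
- **Specific Populations, Gender.** Reconcile this paragraph with inclusion 2 and Section 1.4, so that one statement of the eligible sexes remains.

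The cost is one inexpensive test for a subset of the women and possibly a few exclusions. The target sample size is unaffected.

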4.3 Subject Withdrawal

Subjects may withdraw at any time for any reason. In the event the principal investigator or the site monitor believes a subject is at risk of injury the subject will be withdrawn from the study and:

- (a) If the subject has not completed the study
- (b) The subject will be replaced with another subject

- (c) The PI will follow-up with the subject every day for 14 days
- (d) The information will be reported in the appropriate CRF

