1.4. Population

This is a multi-center study to be conducted at hospital sites. This exact protocol will be followed. There will be one or more PIs. The study will be approved by each hospital's Ethics Committee.

The population for this study will be hospitalized COVID-19 male patients 18 years or older of any ethnicity. Approximately, 300 male subjects who meet all the eligibility criteria will be enrolled. The estimated time from screening to end of the study for each subject is approximately 14 days.

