6.2 Method and Timing

The assessments, as described in section 6.1, will occur as follows:

I. Physical Examination

The assessment will occur at screening. The information will be recorded in the appropriate CRF.

II. Clinical Laboratory Evaluations:

The assessment will occur upon admission to the hospital as well as at day 14. Additional laboratory tests or timing may be ordered as deemed necessary by the PI.

III. Adverse Events:

Adverse events will be assessed daily during the 14-day duration of the trial. The information will be recorded in the appropriate CRF.

The methods employed for completing assessments are described in section 6.1

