1.4. Population

This is a multi-center study to be conducted at hospital sites. This exact protocol will be followed. There will be one or more PIs. The study will be approved by each hospital's Ethics Committee.

The population for this study will be hospitalized COVID-19 patients 18 years or older of any ethnicity. Approximately, 600 (300 males and 300 females) subjects who meet all the eligibility criteria will be enrolled. The estimated time from screening to end of the study for each subject is approximately 28 days.

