3.1 Primary Study Endpoints/Secondary Endpoints

Primary Outcome Measure:

1. Treatment efficacy of Proxalutamide relative to placebo arm as assessed by the COVID-19 ordinal scale (defined in Section 5.1) [Time Frame: Day 14]

Secondary Outcome Measures:

1. Treatment efficacy of Proxalutamide relative to placebo arm as assessed by the COVID-19 ordinal scale (defined in Section 5.1) [Time Frame: Day 28]
2. Time to recovery [Time Frame: Day 1 through Day 28]
Recovery is defined as the first day on which the subject satisfies one of the following two categories from the ordinal scale (defined in Section 5.1): 2) Not hospitalized, limitation on activities and/or requiring home oxygen; 1) Not hospitalized, no limitations on activities.
3. Proportion of death [Time Frame: Day 1 through Day 28]
Defined as the number of subjects who have died in each arm divided by the numbers of subjects randomized to the treatment arm
4. Duration of new oxygen use [Time Frame: Day 1 through Day 28]
Duration of new oxygen use measured in days among subjects that did not require oxygen upon randomization.
5. Proportion of subjects testing positive for SARS-CoV-2 [Time Frame: Day 14]
Defined as the proportion of subjects in each arm with a qualitative positive rtPCR SARS-CoV-2 test from upper respiratory tract specimens

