6.3.7 Time Period and Frequency for Event Assessment and Follow-Up

For this study, all Grade 3 and 4 AEs and all SAEs occurring from the time the informed consent is signed through the Day 28 (end of study) visit will be documented, recorded, and reported.

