Treatment efficacy of Proxalutamide relative to placebo arm as assessed by the COVID- 19 ordinal scale (defined in Section 5.1) [Time Frame: Day 28]	A clear cut-off point was used in the COVID-19 scale (scores 1 and 2) so that we were able to measure the effect size recovery ratio [time frame: 28 days].	All scores at Day 28 are informative and is better presented in a graph. As reported for the primary outcome, we clarified a measure of effect within this secondary outcome measure.
Time to recovery [Time Frame: Day 1 through Day 28] Recovery is defined as the first day on which the subject satisfies one of the following two categories from the ordinal scale.1): 2) Not hospitalized, limitation on activities and/or requiring home oxygen; 1) Not hospitalized, no limitations on activities.	Name changed to post-randomization time to recover/alive hospital discharge [time frame: day 1 to day 28] in median days (interquartile range). Recovery was defined as the first day on which the subject reached scores 1 and 2 in the COVID-19 ordinal scale.	We needed to be more specific in this outcome to make it clearer and reproducible.
Proportion of death [Time Frame: Day 1 through Day 28] Defined as the number of subjects who have died in each arm divided by the numbers of subjects randomized to the treatment arm	Name changed to 28-day all-cause mortality rate . The proportion of patients who reached score 8 in the 19-COVID ordinal scale after randomization. [Time frame: 28 days]	The outcome is still the same described in the statistical plan of the final protocol, however we just clarified that it refers to all-cause mortality. All-cause mortality is a more stringent measure, and therefore this change goes against the direction of the bias. Although mortality at 14 days could be contemplated in the original Primary outcome (score 8), we decided to analyze mortality at 28 days only, which is more stringent and reflects the intention-to-treat.
Duration of new oxygen use [Time Frame: Day 1 through Day 28]	Excluded	This outcome measure was not adequately reported by the hospital sites, and therefore we have not included it in the final statistical plan.
Proportion of subjects testing positive for SARS-CoV-2 [Time Frame: Day 14]	Excluded	This outcome also needed to be abandoned because we lacked financial resources to test all patients again for SARS-CoV-2 at day 14.

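### Section 4.3(c) follows investigator-withdrawn subjects for only 14 days, in conflict with the Day-28 score, 28-day mortality and Day-28 safety windows

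*Combined protocol and SAP*

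**What the plan says.** Section 4.3 of the current protocol (the version with the female cohort) lets subjects leave voluntarily, and then adds a second route, removal from the study (the quote is cut before its last words): "In the event the principal investigator or the site monitor believes a subject is at risk of injury the subject will be withdrawn from the". For that second route it provides for replacement (b) and for follow-up (c): "The PI will follow-up with the subject every day for 14 days". The start of the 14 days is not given. No follow-up is stated for voluntary withdrawal.

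The same sentence stands in section 4.3 of the male-only protocol. There, section 1.4 says "The estimated time from screening to end of the study for each subject is approximately 14 days", and section 6.2 says "Adverse events will be assessed daily during the 14-day duration of the trial". In the current protocol, section 1.4 says "The estimated time from screening to end of the study for each subject is approximately 28 days", and the windows for outcome assessment (3.2), likely transfer (4.2), daily scoring (5.2) and adverse events (6.2) have also moved from 14 to 28 days. Section 4.3(c) has not.

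The outcomes that need Day 28 are in section 3.1: the Day-28 ordinal score, time to recovery, and death from Day 1 to Day 28, the last "Defined as the number of subjects who have died in each arm divided by the numbers of subjects randomized to the treatment arm". The Final Statistical Plan (part 2, Secondary Outcome Measures) restates mortality as "The proportion of patients who reached score 8 in the 19-COVID ordinal scale after randomization. [Time frame: 28 days". On safety, section 6.3.7 sets one window for severe (Grade 3 and 4) and serious events: "all SAEs occurring from the time the informed consent is signed through the Day 28 (end of study) visit will be documented, recorded, and reported". Section 7.3 bases the primary analysis on intent-to-treat and says that all enrolled subjects are analysed.

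**The concern.** Section 4.3 is the only place that says what happens to the follow-up of a subject removed by the investigator or monitor, and it describes leaving the study and being replaced, not merely stopping treatment. A site could reasonably read it as permission to stop after 14 days.

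The reason for removal is a perceived risk of injury, so missing data here would be related to prognosis and possibly to the drug. The mortality measure divides deaths seen by everyone randomized, and both the protocol (7.1) and the Final Statistical Plan say only that missing data are described or reported. Without a rule for unknown vital status, a death nobody saw stays in the denominator as a non-death. In the Cox model for death, the same subjects would presumably be censored at last contact, and that censoring would be informative. The 28-day recovery ratio and the safety table could lose the same people. Any bias would follow the arm with more such withdrawals, and its direction cannot be known in advance.

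**Working it through.** The plan gives no derived figure to reproduce here. The check is calendar arithmetic on stated windows.

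**Inputs.** Follow-up after removal: 14 days (4.3(c)). Last outcome day: 28 (3.1, 5.2, 6.3.7). Treatment: 14 days (3.2). Non-completion: 3.5% (7.2). Size: 294 per cohort, about 600 in all (7.2).

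**Step 1: last day observed.** Let d be the day of removal. Because the start of the clock is not stated, three readings are possible:

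- A, the 14 days start the day after removal: last day = d + 14, shortfall = 28 − (d + 14) = 14 − d.
- B, the day of removal counts as the first of the 14: last day = d + 13, shortfall = 15 − d.
- C, the 14 days run from enrollment: last day = 14, shortfall = 14 for everyone.

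| Removed on | A: last day (short by) | B: last day (short by) | C: last day (short by) |
|---|---|---|---|
| Day 2 | 16 (12) | 15 (13) | 14 (14) |
| Day 5 | 19 (9) | 18 (10) | 14 (14) |
| Day 10 | 24 (4) | 23 (5) | 14 (14) |
| Day 13 | 27 (1) | 26 (2) | 14 (14) |
| Day 14 | 28 (0) | 27 (1) | 14 (14) |

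Under A, every removal before Day 14 falls short of Day 28; under B, every removal before Day 15; under C, all of them. Since treatment lasts 14 days, nearly all on-treatment removals are affected on any reading.

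**Step 2: the Day-14 primary endpoint.** The earliest possible removal is Day 1, which gives a last day of 15, 14 and 14 under A, B and C. Day 14 is reached in each case. The sample size also does not depend on this clause.

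**Step 3: how many subjects.** The documents do not say how many removals to expect. As an assumption, if all 3.5% non-completers were of this kind: 0.035 × 294 = 10.3 per cohort and 0.035 × 600 = 21 overall. At 1% to 10%, the range is 2.9 to 29.4 per cohort.

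**Step 4: what unknown vital status can do.** With n randomized in an arm, D deaths seen and m subjects of unknown Day-28 status, the plan's figure is D/n, while the true proportion lies between D/n and (D + m)/n. The width is m/n. If all of an assumed 3.5% were unknown, the width would be 3.5 percentage points. That is an outer limit, reached only if every such subject died unseen.

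**The case against.** The strongest answer is that other sections already require the data. Section 6.3.7 runs through Day 28 for Grade 3 and 4 AEs and all SAEs, with no exemption for removed subjects. Section 6.3.2 makes death an SAE and requires SAEs to be followed until they resolve or stabilize. Section 6.3.9.1 asks sites to report SAEs learned of even after the study. Section 5.2 plans a visit or call at Day 28 for discharged subjects, with a missing entry otherwise. Section 7.3 analyses all enrolled subjects.

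This stands as a limit. A reader might infer that removed subjects are lost to Day-28 data. The documents do not support that: deaths and serious events are formally required elsewhere, so what exists is a contradiction. It does not remove the point, because those sections are general, section 6.3.7 is tied to a Day-28 visit that nothing says a removed subject will have, and section 5.2 does not mention removed subjects. The Day-28 score has the least protection.

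Two further limits also stand. The 14-day clause does not cover everyone who withdraws. Voluntary withdrawal has no stated follow-up, and section 3.6, which discontinues subjects after an SAE or a Grade 3 or 4 AE, neither refers to 4.3 nor states a follow-up. Nor is the clause simply a remnant of a 14-day study: the male-only protocol already gave a 28-day duration (3.5) and Day-28 secondary outcomes (3.1), so the mismatch existed there too. The identical wording makes carry-over likely, but that is an inference.

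**Conclusion.** The point holds as an internal contradiction that puts Day-28 secondary and safety data at risk in a group selected on prognosis. If the clock starts at withdrawal, literal use of 4.3(c) ends observation 1 to 13 days early for removals on Day 13 back to Day 1. The Day-28 ordinal score is most exposed; mortality and serious safety data are exposed only if sites follow 4.3(c) in preference to section 6.3.7. The primary endpoint at Day 14 and the sample size are essentially unaffected.

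The size is not known. About 21 of 600 rests on the assumption that every non-completer is a removal by the investigator or monitor, although the 3.5% is an overall non-completion figure taken from another trial. A reader might go further and estimate hidden deaths: if 10% to 50% of the 21 died after the window, that would be 2.1 to 10.5. The documents give no such fraction, it would apply to people who had already survived 14 days after removal, and it presumes that none of the deaths was captured as an SAE. No count of deaths should be quoted.

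**What to change.** Reconcile section 4.3(c) with sections 3.6, 5.2, 6.3.7 and 7.3. State that any subject who is withdrawn or discontinued stays under observation through Day 28 after randomization, with the Day-28 score, vital status and AEs/SAEs collected as for everyone else, by phone if discharged, unless the subject withdraws consent to follow-up. Counting from randomization also settles the undefined start of the clock. Make clear that a replacement under 4.3(b) does not take the removed subject out of the intent-to-treat population. This concerns data collection only; when to withdraw a subject is not at issue.

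In the Final Statistical Plan, say that unknown Day-28 vital status is not counted as survival, report the number unknown by arm, and add a sensitivity analysis, for example the bounds D/n to (D + m)/n in each arm.

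That plan describes itself as adjusted during manuscript writing, so for subjects already completed an amendment cannot restore visits. For them, retrieve Day-28 vital status where possible and report the remaining unknowns by arm.

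The cost is a short amendment and, for subjects still in follow-up, at most 14 more days of phone or chart checks for what is expected to be a small number of people, plus the retrieval work.
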